Due to the high cost of sugammadex, some researchers have hypothesized that a lower dose is required when combined with neostigmine. A 2015 study from Beirut in adults undergoing elective surgery demonstrated that a dose of 2 mg/kg of sugammadex combined with neostigmine 0.05 mg/kg was non-inferior to the standard dose of 4 mg/kg of sugammadex in reversing deep NMB, defined as returning from a TOF count of 0 to a TOF ratio of 0.9 within 5 minutes, with similar times to extubation as well as no cases of recurarization in the post anesthetic care unit (PACU) (16). Lobaz, Sammut and Damodaran reported in 2013 the use of sugammadex as rescue therapy for a 71-year-old patient with end stage renal disease who was unable to be weaned off the ventilator almost five hours after receiving a single 1.2 mg/kg dose of rocuronium. He had initially achieved a TOF of 4, was reversed with 2.5 mg of neostigmine 45 minutes after induction, but failed to maintain adequate spontaneous ventilation despite his TOF remaining at 4, and was transferred to the intensive care unit 3 hours post induction. There, his TOF steadily declined to 2, as a result of which he received a 6 mg/kg dose of sugammadex, causing him to be successfully extubated ten minutes later (17). It is similarly important to dose sugammadex appropriately; Carollo et al. published a case report in 2019 of an 8-month-old patient who had recurarization after a 4 mg/kg dose of sugammadex was given with a TOF count of 2/4, which fortunately resolved after a second 4 mg/kg dose of sugammadex (18).

Lastly, known common adverse effects of neostigmine include bradycardia, nausea and vomiting (19), while the use of sugammadex has been found to lead to nausea, vomiting, hypotension and headache in \geq 10% of patients (5). There have also been case reports of marked bradycardia possibly leading to cardiac arrest with the use of both agents.

Page 6 of 30 Version: 3 (10/14/2024)

4. Study Endpoints

Primary study outcome:

The time taken to achieve a TOF ratio of 0.9 after the use of the intervention drug versus placebo in a patient population that has already received neostigmine for NMB reversal.

Secondary study outcome:

The percentage of patients who achieve a TOF ratio of 0.9 within 1 minute, 2 minutes, 5 minutes, and 10 minutes.

Safety outcomes:

The incidence in PACU (measured in %) of:

- i. Nausea,
- ii. Vomiting,
- iii. Bradycardia²,
- iv. Tachycardia³, and
- v. Hypotension⁴.

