For the safety outcomes, patients who were recruited but did not receive the intervention drug will be compared to patients who did receive the intervention drug to determine if their rates of adverse effects are similar. However, the sample size in this study is too low to perform formal non-inferiority tests on this data.

5. Study Intervention/Investigational Agent

Study intervention:

Patients will be randomized to six groups: 2 mg/kg (the lowest dose approved by the FDA), 1 mg/kg, 0.5 mg/kg, 0.25 mg/kg, 0.125 mg/kg of sugammadex and placebo (normal saline).

The Grady Memorial Hospital operating room pharmacy will store and dispense the study drug, while the anesthesia provider in the operating room will administer it.

As elaborated before, sugammadex is a FDA-approved drug that is in routine clinical use for NMB reversal.

Page 7 of 30 Version: 3 (10/14/2024)

² Heart rate < 60 beats per minute over two or more recordings if not present pre-operatively

³ Heart rate > 100 beats per minute over two or more recordings if not present pre-operatively

⁴ Systolic blood pressure < 90 mmHg and/or mean arterial pressure < 65 mmHg over two or more recordings

The study protocol was submitted to the U.S. FDA, and found to be exempt from IND regulations (PIND 162798 dated 2022-Jul-13).

6. Procedures Involved

This project is a double-blind randomized placebo-controlled dose-response trial that aims to determine the time taken to achieve adequate reversal comparing five doses of sugammadex as rescue therapy following inadequate reversal with neostigmine.

We will identify patients in the Grady Memorial Hospital OR who are scheduled to undergo an elective surgery under general anesthesia, received rocuronium for NMB and neostigmine for NMB reversal, and achieved a TOF count of at least 3 twitches but not a TOF ratio of 0.9 fifteen minutes after neostigmine has been given.

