These patients will be randomized using the Emory University REDCap (Research Electronic Data Capture) software to six groups: 2 mg/kg (the lowest dose approved by the FDA), 1 mg/kg, 0.5 mg/kg, 0.25 mg/kg, 0.125 mg/kg of sugammadex and placebo. Doses would be based on actual body weight. The time taken to reach a TOF ratio of 0.9 thereafter would be measured. If the patient fails to achieve this goal by 10 minutes, sugammadex would be given in 2 mg/kg increments until the patient reaches this threshold and can be safely extubated. The TOF ratio would be measured again at 30 minutes after arrival at the PACU to exclude delayed residual NMB with the plan to give further 2 mg/kg doses of sugammadex if detected.

The inclusion of a placebo group would allow us to examine if patients may recover spontaneously over that time without needing any sugammadex at all, and what parameters may predict that subset of patients. It will also improve the dose response modelling, in that randomization has been weighted so that patients who are least likely to need sugammadex (i.e. if they achieved a TOF count of 4 twitches without fade) are more likely to be in the placebo group or at the lowest dose of sugammadex that is being tested.

The time taken to a TOF ratio of 0.9 after the intervention drug has been given would be compared for statistically significant differences, controlling for the:

- TOF count (3 twitches, 4 twitches with fade, 4 twitches without fade), and
- TOF ratio (0 to < 0.9)

15 minutes after neostigmine has been given and prior to giving the intervention drug.

Quantitative neuromuscular monitoring will be carried out using electromyography, which measures the TOF ratio every 20 seconds. The TOF count (between 0 to 4) and the TOF ratio (0 to 1) would be measured and recorded at baseline and after administration of the study drug. If the TOF ratio remains < 0.9 after this, or if the patient exhibits any symptoms or signs of residual NMB blockade, a further 2 mg/kg dose of sugammadex would be given until the patient achieves a TOF ratio of 0.9.

Page 8 of 30 Version: 3 (10/14/2024)

7. Statistical Analysis Plan

Power Analysis

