Review our Data and Safety Monitoring Questionnaire and insert the relevant monitoring table at the end of this section. Also upload the completed questionnaire in the "Basic Study Information" smartform section in eIRB, question #8, as a separate document.

| S | Select one of the following: | | |
|---|------------------------------|--|--|
| | ☐ Medium Complexity | | |
| | ☐ High Complexity Category A | | |

The study team will review the safety endpoints (nausea, vomiting, bradycardia, hypotension) on a monthly basis for the duration of the study. These safety endpoints are collected at each study visit and recorded in the study database. Patients are routinely assessed for these side effects in the PACU by their bedside nurse as well as the anesthesia resident who is responsible for discharging them from the PACU.

| | | Subgroup n=6 | | Total N=36 | |
|-------------|---|--------------|---------------------|------------|---------------------|
| Event | Assumed Probability Risk (upper end) | p<0.01 | Safety cut short if | p<0.01 | Safety cut short if |
| Nausea | | | | | |
| (high) | 0.25 | p=0.0046 | n≥5 | p=0.0086 | n≥16 |
| Vomiting | | | | | |
| (high) | 0.15 | p=0.0059 | n≥4 | p=0.0048 | n≥12 |
| Bradycardia | | | | | |
| (high) | 0.05 | p=0.0022 | n≥3 | p=0.0083 | n≥6 |
| Hypotension | | | | | |
| (high) | 0.15 | p=0.0059 | n≥4 | p=0.0048 | n≥12 |

Using the binomial equation (see below), we calculated the probability of seeing a set number of patients in each group, if the actual probability in the normal surgical population is at the level specified in the 'assumed probability' column.

For example, if the 'normal' probability of nausea is up to 25% (that is, the risk with treatment is the same as the risk under standard surgical conditions), then the chance of having 5 or more patients with nausea in any one treatment group is 0.0046, and the chance of having 16 or more patients with nausea in total is p=0.0048. Since this is unlikely, we will reject the null hypothesis, and conclude that the actual risk in our trial is actually higher than that. So if 5 or more patients report nausea in any one group or if 16 or more patients report nausea in total, this would trigger a suspension of the trial for further review.

Page 15 of 30 Version: 3 (10/14/2024)

$$P(X \ge x) = \sum_{x}^{N} {N \choose x} p^{x} (1-p)^{(N-x)}$$

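### Bradycardia, tachycardia and hypotension are defined as safety outcomes only in PACU, so an episode that begins and resolves in the operating room after the study dose falls outside the defined rates, and Section 21 leaves unclear whether it counts toward the stopping limits

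*Combined protocol and SAP*

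**What the plan says.** Section 4 introduces the five safety outcomes as "The incidence in PACU (measured in %) of" nausea, vomiting, bradycardia, tachycardia and hypotension. The footnotes define bradycardia as "Heart rate < 60 beats per minute over two or more recordings if not present pre-operatively" and hypotension as "Systolic blood pressure < 90 mmHg and/or mean arterial pressure < 65 mmHg over two or more recordings". They set no time window, so the window comes from the Section 4 lead-in.

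Section 5 says of the study drug that "the anesthesia provider in the operating room will administer it". Section 6 then has the TOF ratio followed, and states: "If the patient fails to achieve this goal by 10 minutes, sugammadex would be given in 2 mg/kg increments".

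The Section 20 data list has one yes/no entry for the five events, under postoperative details, and no OR entry for them.

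Section 21 says: "The study team will review the safety endpoints (nausea, vomiting, bradycardia, hypotension) on a monthly basis". It adds that "Patients are routinely assessed for these side effects in the PACU", and gives numerical limits that would suspend the trial for review. Later in the same section, serious and other adverse events are to be collected up to PACU discharge, for participants and for screen failures. Monitoring Table 3 has the principal investigator review adverse events monthly.

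Section 3 gives the protocol's own reason for interest in heart rate: "There have also been case reports of marked bradycardia possibly leading to cardiac arrest with the use of both agents".

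**The concern.** The interval that begins at injection is the one the defined safety rates leave out. It is also the only interval in which no randomized patient has yet had sugammadex beyond the assigned dose. By PACU arrival, a placebo or low-dose patient who did not recover will have received rescue sugammadex, so PACU rates by arm mix assigned dose with rescue.

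If OR episodes are also left out of the Section 21 counts, the stopping rule would be less sensitive to a haemodynamic problem that is over before PACU. If they are included, the limits would be applied to a longer window than the one Section 4 defines. The plan does not say which applies.

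**Working it through.** **1. Is an OR-only episode inside the defined outcome?**

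- Place of dosing: the OR (Section 5).
- Observation after dosing: up to 10 minutes before the timed rescue step, then possible 2 mg/kg increments and extubation, all before PACU (Section 6).
- Outcome window: PACU (Section 4). Form entry: postoperative only (Section 20).

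An episode that starts after injection and resolves before PACU meets no part of the Section 4 wording. One that persists or recurs over two PACU recordings does count. Section 20 says in general terms that data are collected in both the OR and PACU, but this does not alter the outcome window.

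**2. Is it captured elsewhere?** Possibly. Section 21 collects serious and other adverse events up to PACU discharge. That route has no stated start time, no requirement to use the footnote definitions and no threshold.

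**3. Does it count toward the stopping limits?** Section 21 refers to the safety endpoints, which Section 4 places in PACU, and describes assessment there. It does not say that only PACU events count. The text is unclear.

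**4. The plan's own figures.** Section 21 uses P(X ≥ r) = Σ C(n,x) pˣ(1−p)ⁿ⁻ˣ, summed from r to n.

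- Bradycardia, p = 0.05, at least 3 of 6: 20(0.05³)(0.95³) + 15(0.05⁴)(0.95²) + further terms = 0.00214 + 0.00008 + … = 0.0022. At least 6 of 36: 0.0083.
- Hypotension, p = 0.15, at least 4 of 6: 15(0.15⁴)(0.85²) + 6(0.15⁵)(0.85) + 0.15⁶ = 0.00549 + 0.00039 + 0.00001 = 0.0059. At least 12 of 36: 0.0048.

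All four agree with the table. The arithmetic is sound; the open question is which events enter the count. Tachycardia has no limit in the table.

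**5. How much could the window matter?** The documents give neither the risk over the whole period nor the share seen in PACU, so both are assumptions. Let q be the true risk from injection to PACU discharge, and c the share of affected patients who also meet the definition in PACU. The chance of reaching the total limit is the same binomial tail with p = q × c:

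| Event and limit | q | c = 1 | c = 0.75 | c = 0.5 | c = 0.25 |
|---|---|---|---|---|---|
| Bradycardia, ≥ 6 of 36 | 0.10 | 0.15 | 0.05 | 0.008 | 0.0002 |
| Bradycardia, ≥ 6 of 36 | 0.20 | 0.75 | 0.46 | 0.15 | 0.008 |
| Bradycardia, ≥ 6 of 36 | 0.30 | 0.98 | 0.85 | 0.46 | 0.05 |
| Hypotension, ≥ 12 of 36 | 0.30 | 0.39 | 0.09 | 0.005 | < 0.0001 |
| Hypotension, ≥ 12 of 36 | 0.40 | 0.84 | 0.39 | 0.04 | 0.0001 |

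For one group at c = 1, 0.75, 0.5 and 0.25, the chances are 0.099, 0.047, 0.016 and 0.002 for bradycardia (q = 0.20, at least 3 of 6). For hypotension (q = 0.40, at least 4 of 6) they are 0.18, 0.07, 0.017 and 0.001.

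The table reads both ways. If q reflects drug harm, a PACU-only count loses sensitivity. If q is background under anaesthesia, counting OR events against the present limits could suspend the trial without any drug effect: at a background bradycardia risk of 0.20, with probability 0.75.

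**6. What could an OR outcome show?** There are 6 patients per arm. Even 0 events in 6 leaves a one-sided 95% upper limit of 1 − 0.05^(1/6) = 0.39. It can only be descriptive.

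**The case against.** Safety oversight of the OR period is not absent. Section 21 names perioperative cardiac arrest among the serious events, collects other adverse events up to PACU discharge, and has the principal investigator review data as they are collected and adverse events monthly. A reader might infer that OR bradycardia goes unrecorded; the documents do not support that. What is missing is a defined rate.

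A reader might also infer that the stopping rule is explicitly PACU-only. Section 21 implies this through its reference to the safety endpoints and its account of who assesses them, but does not say it.

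The planned safety comparison in Section 4 is between recruits who received the intervention drug and those who did not, and the protocol concedes that the sample is too small for formal non-inferiority tests. PACU is a window both groups share. Untreated recruits have no injection time, so moving the start of the existing outcome to injection would add observation time for one group only. It would also put anaesthetic background into limits set at 5% and 15%. Both objections stand, and they are why the OR outcome should be separate.

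Three further inferences are not supported:

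- That most of what PACU counts follows rescue. No rescue rate is given. The 2013 trial cited in Section 3 reports mean recovery to a TOF ratio of 1.0 in 1.8 to 4.1 minutes at 0.5 to 2.0 mg/kg, doses assigned to 18 of the 36 patients, though in a different setting.
- That before rescue the arms differ only by dose. Table 1 weights allocation by TOF count: across the strata 4 twitches without fade, 4 with fade and 3 twitches, placebo has 3, 2 and 1 patients and 2 mg/kg has 1, 2 and 3.
- That events cluster soon after injection. The documents give no onset times.

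**Conclusion.** The point holds in a limited form. By the wording of Sections 4 and 20, a haemodynamic episode confined to the OR is outside the defined safety rates, although it may appear as an adverse event without the footnote definitions or a threshold. Whether it counts toward the Section 21 limits is unclear. The uncounted period is up to 10 minutes before timed rescue, plus any rescue and the time until PACU. Its effect on event rates cannot be sized from the documents; the stopping-rule probabilities above rest entirely on assumed q and c. The printed limits are computed correctly for their assumed risks. The change is worth making because Section 3 itself raises marked bradycardia, because PACU rates by arm are exposed to rescue dosing, and because a separate OR outcome leaves the planned comparison and the limits undisturbed.

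**What to change.** 1. Keep the PACU outcomes in Section 4 for the treated-versus-untreated comparison and for the existing limits.
2. Add a separately reported OR outcome for randomized patients, by assigned dose: bradycardia, tachycardia and hypotension by the same footnote definitions, from study-drug injection to first rescue dose or leaving the OR, whichever is earlier. Label it descriptive.
3. Add matching fields to the Section 20 data form.
4. State in Section 21 whether OR events count toward the limits. If they do, justify the assumed risks (0.05 for bradycardia, 0.15 for hypotension) for the wider window and recalculate the limits.
5. If untreated recruits are to be compared in the OR window, define a matching start time for them.

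Cost: some extra data abstraction and no new visit, assuming routine OR heart rate and blood pressure records are available. The documents give no recording interval, so the two-recordings criterion may span different durations in the OR and PACU; the report should give the interval. Background event rates will be higher under anaesthesia, and with 6 patients per arm the OR results will not support inference between doses.

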An *a priori* power analysis was conducted using G*Power 3.1.9.4 (20). We used an ANOVA F-Test for one-way omnibus difference between groups, alpha threshold of 0.05 for rejecting the null hypothesis, statistical power of 0.80 and a "very large" effect size of 0.765 was calculated based on results from a 2013 randomized controlled trial that examined time from TOF count = 4 to TOF ratio 1.0 comparing neostigmine to three different doses of sugammadex: 0.5, 1.0, and 2.0 mg/kg (15). This gave a required sample size of N=24. This number was increased to N=36 to account for patients with poor modeling from a high starting TOFR (resulting in few data points for that patient) or incomplete recovery within the maximum ten minutes allotted. An anticipated 70% of those enrolled will become ineligible because of an initial TOFR of 90% or greater, thus not requiring any medications, so up to 120 patients may need to be recruited and screened, but only 36 will receive any treatment.

Methodology

Randomization will occur with permuted block randomization, divided into 18 groups, to ensure proportional allocation of participants in each group over time. Dose randomization will be assigned after stratifying by initial TOFC, with a set number of patients recruited for each group, as seen the table below. This ensures that patients who likely need a lower dose are more likely to receive it. Randomization will not occur until participation is assured, i.e., their TOFR is <0.90.

Table 1: Randomization plan for patients (n=36)

| Sugammadex Dose (mg/kg) → | | 0.00 | 0.125 | 0.25 | 0.50 | 1.00 | 2.00 | | | |
|---------------------------|-----------------|------|--|----------|------------|---------|---------|------|-------|----|
| Initial TOFR | Initial TOFC | Fade | placebo | | | | | | Total | |
| ≥ 0.9 | NA | NA | No treatment; track for adverse events | | | 0 | | | | |
| | | 4 | No | 3 pt | 3 pt | 2 pt | 2 pt | 1 pt | 1 pt | 12 |
| < 0.9 | 4 | Yes | 2 pt | 2 pt | 2 pt | 2 pt | 2 pt | 2 pt | 12 | |
| | 3 | NA | 1 pt | 1 pt | 2 pt | 2 pt | 3 pt | 3 pt | 12 | |
| < 0.9 | 0-2 | NA | No t | treatmen | t; track f | or adve | se even | ts | 0 | |
| Total # of Patients (pt) | | | 6 | 6 | 6 | 6 | 6 | 6 | 36 | |

Statistical Methodology

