- Did not require general anesthesia for surgery,
- Did not require NMB,
- Did not receive neostigmine for NMB reversal,
- Had a TOF count < 3 or a TOF ratio ≥ 0.9 fifteen minutes after neostigmine, or
- Remained intubated in the immediate postoperative period.

As the study intervention is a one-time dose of the study drug in the OR, no further action should be required if the patient decides to later withdraw from the study. The study will be terminated when the number of participants has reached the required threshold.

17. Risk to Participants

The most common risks of sugammadex as listed by the FDA (5) include:

- Nausea (23-26%)
- Vomiting (11-15%)
- Pain (36-52%)

Uncommon but serious risks of sugammadex include:

- Hypotension (4-13%)
- Tachycardia (2-5%)

Page 12 of 30 Version: 3 (10/14/2024)

- Bradycardia (1-5%)
- Anaphylaxis (0.3%)

Notably, all of these are known to be risks of general anesthesia as well as surgery and are routinely monitored for and treated in the PACU.

18. Potential Benefits to Participants

All study subjects will have any residual NMB reversed, which will prevent any postoperative complications such as respiratory compromise or weakness.

19. Compensation to Participants

N/A

20. Data Management and Confidentiality

Data to be collected include:

- Baseline demographics: MRN, date of birth, sex (male/female), race (white, black, American Indian or Alaska Native, Asian, Native Hawaiian or Other Pacific Islander, two or more races), ethnicity (Hispanic or Latino, not Hispanic or Latino), weight (kg)
- ii. Preoperative details: ASA status (I-IV)
- iii. Surgery details: date of surgery, diagnosis, surgery, start case time (hr: min), end case time (hr: min)
- iv. Anesthesia details: if succinylcholine was used (Y/N), total amount of rocuronium given (mg), the last dose of rocuronium that was given (mg), the time that the last dose of rocuronium was given (hr:min), neostigmine dose (mg), the time that neostigmine was given (hr: min), the time that the study drug was given (hr: min).
- v. TOF ratio (0-1)
 - Before any paralytic is given at the start of the case
 - Before neostigmine is given at the end of the case
 - Before the study drug is given
 - 30 minutes after PACU arrival
- vi. TOF count (0-4 ± fade)
 - Before neostigmine is given at the end of the case
 - Before the study drug is given
- vii. The time taken to achieve a TOF ratio of 0.9 (seconds).

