- viii. Postoperative details: if there was any of the following adverse effects: nausea, vomiting, bradycardia, tachycardia, hypotension (Y/N).

Page 13 of 30 Version: 3 (10/14/2024)

Baseline demographics and postoperative complications will be collected for patients who were enrolled but did not meet the study inclusion criteria to receive the intervention drug and their data will be used as a control group for the safety outcomes.

The data collection form is in the Emory University REDCap database but a similar form has been attached to this protocol as an Excel spreadsheet. Data would be collected by the study team in the OR and PACU. Data will be stored on the Emory University REDCap and OneDrive databases and may also be sent confidentially between study team members through the Emory University Outlook email network. The REDCap and OneDrive databases as well as the Outlook email network are all secure, encrypted and password protected. Paper consent forms will be stored in a locked box in the principal investigator's office at Grady Memorial Hospital. All data and records will be retained for at least 6 years following study completion.

Results will be reported in an aggregate form and in a de-identified manner. The form with protected health information (date of birth, date of surgery and MRN) will be recorded on a form separate to the form with data to be analyzed. Only study team members will have access to the form that links the study IDs with protected health information. [name], the biostatistician for the Emory University Department of Anesthesiology, will conduct the data analysis in collaboration with the principal investigator.

If a participant declines to participate in all portions of the study, the participant will not be assigned a study ID number and the study team members will refrain from collecting any data on the participant. If the participant agrees to participate in some portions of the study but not others, the participant will be assigned a study ID number and the study team members will be instructed to collect data only on those aspects of the study to which the participant has agreed to participate. These procedures will help prevent unauthorized inclusion of the patient's data in the database.

21. Plans to Monitor the Data to Ensure Safety of Participants and Data Integrity

X More than minimal risk

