Data on serious adverse events such as death, perioperative cardiac arrest, and unplanned hospitalization as well as any other adverse events will also be collected up to the time of PACU discharge for both study participants as well as screen failures (participants who were recruited but not enrolled in the trial due to not fulfilling the study inclusion criteria).

Monitoring Table 3

| DSMP Requirement | How this Requirement is Met | Frequency | Responsible Party(ies) |
|---|--|---|---|
| Real-time review of participant data during | PI will review the data as it is being collected. | Every data collection | PI |
| initial data collection. | being conected. | timepoint | |
| | | Expectation is that this happens every | |
| | | time you obtain information. | |
| Site Monitoring at predetermined intervals: | There should be a standard operating procedure to review | Every 6 months | PI (self-assessment tool) |
| The Principal Investigator has a responsibility to ensure that the study is | data (whether a sample or 100%) at pre-determined intervals to ensure that there is | At a minimum, a review is required annually when no | Delegate a responsible party for each |
| following all aspects of the protocol. | adequate documentation of critical elements such as | one has been enrolled or the | requirement below. Self-assessment is |
| | eligibility criteria. Monitoring is required at the following | study is in long term follow up. | acceptable*. Self-assessment: a |
| | timepoints (but may be done more frequently): • study initiation • at least every six months | Additional risk- based interim monitoring may be required at least | process for self- assessment of protocol compliance and data integrity |
| | while participants are receiving intervention and | once every 12-24 weeks based on the site activity, to | which can be part of an overall DSMP. See CTAC's self- |
| | annually while participants are in follow-up | include the possibility of remote monitoring. | assessment tool on their webpage. |

Version: 3 (10/14/2024)

Page 16 of 30 IRB Form BIO 01192022

| | | A longer frequency | |
|---------------------------|--------------------------------------|-----------------------|--------------------|
| | | could be | |
| | | acceptable with | |
| | | justification about | |
| | | risk to participants. | |
| 100% review of | DCTR will review all regulatory | At study initiation | DCTR |

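### The safety control group in sections 4 and 20 can include patients who never had neostigmine, although every randomized patient has had it

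*Combined protocol and SAP*

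**What the plan says.** All references are to the combined protocol and SAP.

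- **Section 4 (safety outcomes).** The comparison is stated as "patients who were recruited but did not receive the intervention drug will be compared to patients who did receive the intervention drug". The outcomes are nausea, vomiting, bradycardia, tachycardia and hypotension in PACU. The section adds that the sample is too small for formal non-inferiority testing.
- **Section 20.** "Baseline demographics and postoperative complications will be collected for patients who were enrolled but did not meet the study inclusion criteria" to receive the study drug, and "their data will be used as a control group for the safety outcomes".
- **Section 11.** Receiving general anesthesia, rocuronium and neostigmine are each inclusion criteria.
- **Section 16.** The examples of not meeting the criteria begin with "Did not require general anesthesia for surgery". They go on to no blockade, no neostigmine, a disqualifying TOF reading 15 minutes after neostigmine, and remaining intubated.
- **Section 15.** Patients are approached at least a day before surgery, so they are recruited before the reversal agent is known.
- **Section 7, Table 1.** Two untreated rows (TOFR 0.9 or more; TOFR below 0.9 with TOFC 0-2) carry the note "No treatment; track for adverse events".
- **Section 3.** Bradycardia, nausea and vomiting are named as common effects of neostigmine.

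**The concern.** The purpose stated in section 4 is to judge whether adverse effect rates are similar with and without the study drug. That calls for controls who resemble the treated patients in everything else that causes the same events. Every randomized patient has had neostigmine. A recruit whose surgery went ahead without general anesthesia, without blockade or without neostigmine has not, yet sections 4 and 20 count that recruit as a control. A difference in nausea, vomiting or bradycardia could then reflect neostigmine or the anesthetic and not sugammadex.

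The problem may also be hard to repair at analysis. For patients who did not qualify, section 20 names only baseline demographics and postoperative complications. If nothing more is collected, the analyst cannot tell which controls had neostigmine, which had some other reversal agent, or why each was ineligible.

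**Working it through.** **1. Who becomes a control.** Taking the section 16 reasons one at a time:

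| Reason for not qualifying | Neostigmine given? | Control under sections 4 and 20? | Row in Table 1? |
|---|---|---|---|
| No general anesthesia | Not expected | Yes | No |
| No blockade | Not expected | Yes | No |
| No neostigmine | No | Yes | No |
| TOFC below 3, or TOFR 0.9 or more, at 15 minutes | Yes | Yes | Yes |
| Remained intubated | Not stated | Yes | No |

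Withdrawal under section 16 does not take a patient out of the control group. The same list contains the TOFR 0.9 or more patients, who are plainly meant to be controls, and section 21 collects adverse events on all screen failures.

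**2. The plan's own figure.** Section 7 says: "An anticipated 70% of those enrolled will become ineligible because of an initial TOFR of 90% or greater". Then 36 / (1 - 0.70) = 120, which reproduces the stated 120, and 120 - 36 = 84 controls. Since 0.70 x 120 = 84, the whole loss is attributed to TOFR 0.9 or more. The documents therefore supply no count of controls without neostigmine.

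**3. Precision.** Take all 36 randomized patients, placebo included, as the treated group (section 4 does not say whether placebo counts). Use the 25% nausea rate from the section 21 monitoring table. By the normal approximation,

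half-width = 1.96 x sqrt[0.25 x 0.75 x (1/36 + 1/n)].

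- n = 84: 16.9 points
- n = 67: 17.5 points

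With placebo left out (30 v 84) it is 18.1 points.

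**4. Possible shift in the control rate.** If k of 84 controls had no neostigmine and their nausea rate differs by d points, the control rate moves by (k/84) x d. Both k and d are assumptions; d is taken as 5 to 15 points in size.

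- k = 4 (5%): 0.2 to 0.7 points
- k = 8 (10%): 0.5 to 1.4 points
- k = 17 (20%): 1.0 to 3.0 points

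**5. A less favorable assumption.** Suppose unexposed recruits come on top of the 84, as a share s of all recruits. Recruits needed = 36 / [0.30 x (1 - s)], rounded up.

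| s | Recruits | Controls | Unexposed | Shift for d = 5 to 15 |
|---|---|---|---|---|
| 5% | 127 | 91 | 6 (7%) | 0.3 to 1.0 |
| 10% | 134 | 98 | 13 (13%) | 0.7 to 2.0 |
| 20% | 150 | 114 | 30 (26%) | 1.3 to 3.9 |
| 30% | 172 | 136 | 52 (38%) | 1.9 to 5.7 |

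With 136 controls the half-width is 1.96 x sqrt[0.1875 x (1/36 + 1/136)] = 15.9 points, so even the last row stays well inside it. Here the exposed controls still number 84 or 85.

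**6. Sign of the shift.** If unexposed controls had no reversal drug, lower nausea is plausible. But section 5 says sugammadex is in routine use for reversal, and section 17 lists nausea of 23-26% with it. A recruit reversed with sugammadex instead of neostigmine could have much the same rate as an exposed control, or a higher one. The documents do not settle the sign of d.

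**The case against.** The best defense is that few such controls will exist. Section 15 screens for patients likely to have general anesthesia and blockade, section 6 describes identifying patients who have received rocuronium and neostigmine, and section 7 attributes the expected exclusions to a reading taken after neostigmine. The section 20 wording about qualifying to receive the study drug could also be read as pointing to that last reading. This stands as a reason to expect a small effect. It does not close the definition, since no section limits the controls to neostigmine recipients and section 16 lists the wider failures as examples of not meeting the criteria.

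A second defense is that no decision depends on the comparison. This also stands: section 4 disclaims formal testing, the suspension rule in section 21 uses fixed assumed probabilities and not these controls, and the primary and secondary outcomes are unaffected.

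On data collection, the section 20 list is not exhaustive, the REDCap form is not among the documents, and section 21 has case report forms checked against the electronic chart. Exposure might therefore be recoverable. That is why the claim is only that the comparison may not be repairable.

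Three stronger readings might be inferred and are not supported:

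- That Table 1 is a rival definition of the control group. It is a randomization table; it says which rows are tracked for adverse events and does not define a comparison.
- That sugammadex will be made to look worse. That assumes the direction of a bias whose sign is open.
- That safety monitoring is compromised. The suspension thresholds do not use this group.

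**Conclusion.** The point holds as a minor one. As written, sections 4 and 20 admit controls without neostigmine, without blockade or without general anesthesia, and three of the five safety outcomes are common neostigmine effects. The comparison can be biased for a reason unrelated to the study drug.

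The size cannot be taken from the documents. The illustrative shifts run from 0.2 to 5.7 points across the two sets of assumptions, and all are small beside a half-width of about 17 points for nausea. They rest on assumed shares of unexposed controls, an assumed gap of 5 to 15 points in either direction, and the 25% nausea rate. The case for acting is that a cleaner comparison costs almost nothing.

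**What to change.** - In sections 4 and 20, define the safety comparison group as non-randomized recruited patients who had general anesthesia, rocuronium and neostigmine.
- Within it, show the two untreated Table 1 rows (TOFR 0.9 or more; TOFC 0-2) separately.
- For controls, record the reversal agent or agents received, including any non-study sugammadex, and the reason for ineligibility.
- List all other screen failures by reason, with their adverse events, outside the comparison, so that no safety information is lost.
- Label the comparison non-randomized and descriptive.

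The cost is a paragraph of wording, a few data fields and possibly a slightly smaller control group. For illustration, dropping 17 of 84 controls leaves 67 and widens the nausea half-width from 16.9 to 17.5 points. If unexposed recruits come on top of the 84, restriction still leaves about the planned number. Randomization, treatment and sample size do not change.
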